5.4 Efficacy Variables

Bladder Diary Questions

The bladder diary will be completed daily for the 7 days prior to visit 2 and visit 6, to record the number of incontinence episodes and whether these were nocturia events. If a subject has multiple events in 1 day, each event will preferably be entered separately. The number of incontinence pads used will also be recorded in the diary.

Percentage change in number of incontinence episodes in a week

The number of incontinence episodes entered into the eCRF is the total number of events a subject recorded during the 7day period prior to visit 2 and visit 6. This number will be directly used in the calculation of % change in number of incontinence episodes in a week

Number of Incontinence Episodes/24 hours (daily average)

The number of incontinence episodes entered in the eCRF will be divided by 7 to compute the number of episodes/24 hours (daily average). This consideration follows the assumption that the bladder diary will be filled by the subject for the 7 days prior to Visit 2 and Visit 6 and that the patient entered all episodes occurred in this period. Therefore, the following formula will be used:

$$\text{Number of Incontinence episodes / 24 hours} = \frac{\text{Number of incontinence episodes recorded}}{7}$$

Number of Nocturia Episodes in a week

The number of nocturia episodes entered in the eCRF is the total number of nocturia episodes a subject recorded during the 7day period prior to Visit 2 and Visit 6. The value entered in the eCRF will be used in the efficacy analysis of nocturia episodes without any adjustment.

Number of Incontinence Pads per week

The number of incontinence pads entered in the diary represents the number of pads used in a week, therefore the value entered in the eCRF will be used in the analysis without any adjustment.

This consideration follows the assumption that the bladder diary is completed by the subject for the 7 days prior to Visit 2 and Visit 6 and that the patient entered all pads used in this period.

Proportion of subjects who become continent

A subject is defined as continent if he/she has no incontinence episodes.

5.4.1 Sensitivity Efficacy Variables

Sensitivity Analyses will be performed on the number of incontinence episodes in a week as defined in section 5.4.

One set of sensitivity analysis runs efficacy analyses without imputation.

A second set of sensitivity analysis compares the placebo group with the patients in the litoxetine arm at 30 mg who did not have a dose reduction.

A third set of tables will analyse the absolute change of the number of incontinence episodes in a week and the percentage change in the number of incontinence episodes/24 hours.

5.4.2 Exploratory Efficacy Variables

Exploratory Analyses will be performed on the number of incontinence episodes in a week and on the number of incontinence episodes/24 hours as defined in section 5.4.

Based on previous study results with litoxetine, an exploratory analysis will be conducted in subjects with less and more severe UI. Less severe is defined as the population who has incontinence episode frequency below the study median at baseline, while more severe is defined as the population who has incontinence episode frequency above the study median at baseline.

5.5 Baseline

Baseline for all Safety variables including the laboratory parameters will be defined as Visit 2 date. Baseline for all efficacy endpoints will be defined as the last week of the Screening Placebo Run-in Period.

6. Statistical Methodology

6.1 Handling of Missing Data

Missing Data for the Safety Analysis

Partial dates for medications will be imputed. In case of incomplete date, if day and month are missing the first of January is imputed, if only the day is missing the first of the month will be imputed. Completely missing dates will not be imputed.

No other imputation methods are used for missing values in safety variables.

Missing Data for the Efficacy Analysis

The cases where the total number of incontinence episodes is missing will be addressed prior to unblinding with the following multiple imputation process:

1. The imputation method will be applied to the total number of incontinence episodes missing at Visit 6 only.
2. The imputation method will be applied to the number of incontinence episodes only, it will not be applied to the number of pads or to the number of nocturia episodes.
3. The number of imputations will be based on the percentage of missing data.
4. The seed will be set to 1.
5. The imputation process will be applied to the ITT population.

The method of Predictive Mean Matching is proposed for the imputation process. The method imputes the total number of incontinence episodes for each subject with missing value at visit 6. This method does not make an assumption about the distribution of the variables, thereby minimising the risk of assuming normality when not applicable.

With this method a predictive value is computed via a regression model using a set of observed values from cases deemed to be similar to the missing case based on a set of covariates. This methodology is consistent with an assumption of Missing at Random.

For all analyses where the imputation method is used, analyses without imputation will also be performed as sensitivity analyses.

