4.3 Protocol Deviations

In addition to clinical and study conduct protocol deviations which may include deviations to visit procedure, lab testing and patient safety, the following criteria will be considered as protocol deviations:

1. Study drug compliance less than 80% during Treatment Period of the study
2. Not valid efficacy Endpoint value: Number of incontinence episodes not available at Visit 6 (Endpoint).
3. Not valid efficacy Baseline value: Number of incontinence episodes not available at Visit 2 (Baseline).
4. Prohibited medication and medications to be used with caution taken 30 days prior to study entry (Visit 1) onwards. During the Blinded Data Review meeting the Sponsor will evaluate the medications taken from each patient on a case by case basis, determining if major protocol deviations are found, and if so exclude such subject from the ITT or PP population analysis. The adjudication of prohibited and to be used with caution medications will be provided by the Medical monitor. They include:
 - a. Prohibited medications:
 - Nonselective, irreversible monoamine oxidase inhibitors: eg, moclobemide or linezolid
 - CYP1A2 inhibitors like fluvoxamine, ciprofloxacin, or enoxacin since the combination may result in elevated plasma concentrations of litoxetine
 - CYP2D6 inhibitors like bupropion, fluoxetine, metoclopramide, paroxetine or quinidine since the combination may result in elevated plasma concentrations of litoxetine
 - Pimozide and thioridazine since the combination with litoxetine may result in elevated plasma concentration of these compounds
 - Medicinal products containing duloxetine
 - St John's wort or herbal preparations containing St John's wort (*Hypericum perforatum*)
 - Other serotonergic agents: SSRIs, SNRIs, tricyclic antidepressants like clomipramine or amitriptyline, triptans, tramadol, pethidine, and tryptophan
 - Administration of any other medication that would be considered a safety risk for co administration with litoxetine
 - Any pharmacologic agent used to treat symptoms of urinary incontinence
 - b. Medications to be used with caution:
 - Warfarin or digoxin
 - Benzodiazepines, morphinomimetics, antipsychotics, phenobarbital, sedative antihistamines
 - 1c antiarrhythmics (propafenone, flecainide) and metoprolol

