5.1 General, demographic and baseline characteristics

Age (years)

The age will not be recalculated. The values automatically derived in the CRF will be used in the analysis.

Body Mass Index (BMI) (kg/m2)

BMI will not be recalculated. The values automatically derived in the CRF will be used in the analysis.

Previous and Concomitant Medication

Any medication the subject takes from the signature of informed consent and through the duration of the study, other than the study drug, is considered a concomitant medication.

The CRF records all concomitant medications and all medications taken within 30 days prior to Screening.

The medications labelled as 'ongoing' in the 'Prior and Concomitant Medications and Procedures' page in the eCRF will be considered concomitant medications. All other medications are evaluated based on the date: all records with start or end date after the date of signature of the informed consent are labelled as concomitant, other medications are labelled as past.

Past and Concomitant disease

Medical history will be recorded in the CRF. A disease is concomitant if ongoing at Screening visit (i.e. it ended after Screening visit).

A disease is considered as past if it ended prior to the Screening visit.

The diseases labelled as 'ongoing' in the 'Medical and Surgical procedure history' page in the eCRF will be considered concomitant diseases, all other diseases will be defined as past.

Study drug intake

Each dispensing of study drug will be documented in the eCRF.

Date of first randomised study drug intake is the Study Visit 2 date, at which the trial drug is dispensed.

Date of last randomised study drug intake is the date of study visit 6. If this date is missing, the last Study Visit date available will be considered (excluding Visit 1 and Visit 7 dates). The tapering period will not be included to assess the last intake.

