All AEs (excluding SAEs) will be listed, and their time to onset, frequency, severity, and relationship to the trial drug will be tabulated by treatment. Non-TEAEs will be summarised separately from TEAEs.

A subgroup analysis of TEAEs will be presented. Subjects will be divided according to age (under 65, over 65). The SOCs and PTs will be used for tabulation. The number of TEAEs and the number and the percentage of patients with at least one TEAE will be presented by SOC and PT for each treatment group and according to the patient's age.

An additional analysis will explore the TEAEs that lead to study drug reduction. Results will be presented as listings as well as with means of descriptive statistics.

Withdrawals

Premature withdrawals from the trial will be displayed and summarised by primary reason and treatment.

Physical examination

Abnormal physical examination findings will be summarised. For each physical examination a shift table presenting the number and the percentage of patients in each bivariate category (baseline versus Week 8 (Visit 6)) with regards to investigator's interpretation (Normal, Abnormal NCS, Abnormal CS, Not done) will be provided by treatment group.

The other results of targeted physical examination will be only listed.

Concomitant Medications

Concomitant medications will be presented in summary tables and listings. They will be classified according to whether they were taken before the trial (and ongoing into the trial), or started during the trial period. A medication will be defined as concomitant if taken after the date of informed consent.

The following information will be reported for each concomitant medication: generic name, route of administration, start date, stop date, frequency, dosage, and indication.

Prior Medications

Prior medications will be presented in summary tables and listings. Medications will be classified as prior medications if taken before the date of informed consent.

Vital signs

Vital signs will be summarised by treatment group at each visit (Baseline, Visit 3, Visit 4, Visit 5, Visit 6) by means of descriptive statistics and listed by subject.

Parameters collected include:

1. Heart Rate (bpm)
2. Body Temperature (Degree Centigrade)

An additional analysis will be performed also on radial heart rate. The actual change from baseline to each visit (Visit 3, Visit 4, Visit 5, Visit 6) in radial heart rate will be computed.

Past and Concomitant Diseases

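### SAP 6.1 sets partial medication stop dates to the earliest possible day, so some drugs taken after consent are labelled past in the medication tables (minor)

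*SAP*

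**What the plan says.** SAP 6.1 (missing data for the safety analysis) opens with "Partial dates for medications will be imputed". It gives two cases: "if day and month are missing the first of January is imputed", and "if only the day is missing the first of the month will be imputed". It adds "Completely missing dates will not be imputed". Start and stop dates are not treated separately.

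SAP 5.1 uses these dates to sort medications. "The medications labelled as 'ongoing' in the 'Prior and Concomitant Medications and Procedures' page in the eCRF will be considered concomitant medications". For the rest, "all records with start or end date after the date of signature of the informed consent are labelled as concomitant", and whatever remains is past.

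SAP 6.8 gives a definition based on use: a drug used after the consent date is concomitant. It then divides concomitant drugs further: "They will be classified according to whether they were taken before the trial (and ongoing into the trial), or started during the trial period".

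SAP 4.3 item 4 defines the medication deviation by a time window: "Prohibited medication and medications to be used with caution taken 30 days prior to study entry (Visit 1) onwards". The sponsor reviews each patient's drugs individually at the Blinded Data Review meeting, and the medical monitor adjudicates.

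**The concern.** For a start date, the earliest possible day is a common and defensible choice. For a stop date it can only shorten the recorded exposure. Because the SAP 5.1 label depends on whether a date falls after consent, the shortening can change the label.

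Example: consent is on 10 March, and a drug begun earlier is stopped on 25 March and recorded as March. The stop becomes 1 March. No date then lies after consent, so the drug is past, although it was taken for 15 days after consent. SAP 6.8 would call the same drug concomitant, so the two sections disagree.

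Two related faults follow from the same rule:

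- A drug both started and stopped in the consent month, with both days missing, gets the first of the month twice. It is labelled past even if it was used only after consent.
- A complete start date can fall after its own imputed stop. A drug started on 12 March and stopped in March, day unknown, is given a stop on 1 March. SAP 6.1 has no check for this.

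At stake is whether the concomitant medication tables and listings show correctly what subjects took during the study.

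**Working it through.** The documents give no figure on this point, so there is nothing to reproduce. The check counts dates.

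**Inputs from the documents:** the imputation rule (SAP 6.1), the label rule (SAP 5.1), the 30-day look-back (SAP 4.3 item 4), a run-in of 2 weeks, run-in plus treatment of 10 weeks (70 days), and a total study duration of 15 weeks (105 days).

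**Assumptions, not from the documents:** consent is equally likely on each day of a 365-day year (2018 is used) and falls on the Visit 1 date; stop dates are spread evenly over the stated span after consent; the drug was started before consent and is not flagged ongoing; its stop date is partial.

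**Day missing.** The drug becomes past exactly when the true stop is in the same calendar month as consent. In a month of n days, the consent-stop pairs that meet this number 0 + 1 + ... + (n-1) = n(n-1)/2.

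- Seven 31-day months: 7 × 465 = 3,255. Four 30-day months: 4 × 435 = 1,740. February: 378. Total 5,373.
- Stops 1-70 days after consent: 5,373 / (365 × 70) = 5,373 / 25,550 = 21.0%.
- Stops 1-105 days after consent: 5,373 / (365 × 105) = 5,373 / 38,325 = 14.0%.
- Stops 1-14 days after consent: at most 14 pairs count per consent day, so each month gives 91 + 14(n-14). The total is 7 × 329 + 4 × 315 + 287 = 3,850, and 3,850 / (365 × 14) = 3,850 / 5,110 = 75.3%.

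**Day and month missing.** The drug becomes past whenever the true stop is in the same calendar year as consent. A stop k days after consent falls in the next year for k of the 365 consent days.

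- Over 1-105 days the mean k is 53, so 1 - 53/365 = 85.5% are labelled past.
- Over 1-14 days the mean k is 7.5, so 1 - 7.5/365 = 97.9%.

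**Deviation window.** This matters only if the 30-day window were applied to imputed dates.

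- Day missing, drug taken after consent: the imputed stop precedes consent by at most (day of month - 1), which is never more than 30 days. None leave the window.
- Day and month missing, stop 1-105 days after consent: the imputed stop is more than 30 days before Visit 1 in all the same-year cases except those with consent on 1-31 January. That is 85.5% - 31/365 = 85.5% - 8.5% = 77.0%.
- Day missing, drug truly stopped in the 30 days before Visit 1: a direct count over the same year puts about 47% outside the window. These drugs were not taken into the trial.

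**After the change.** If a day-missing stop goes to the last day of its month, or a year-only stop to 31 December, the imputed date is never earlier than the true one. The share of drugs stopped after consent that are labelled past is then 0%.

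**The case against.** A reader might infer that prohibited drugs slip past the deviation check and that subjects stay in the per-protocol set who should not. The documents do not support that. SAP 4.3 item 4 does not use the past/concomitant label. It looks from 30 days before Visit 1 onwards, case by case and blinded, with adjudication by the medical monitor. By SAP 5.1, the eCRF page collects concomitant drugs and drugs from the 30 days before Screening, so a drug labelled past is still in the pool under review. A missing day cannot move a drug taken after consent outside the look-back. A risk would arise only if the window were programmed on imputed dates. The SAP does not say that it will be, and does not rule it out.

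Nor is exposure hidden. SAP 6.5 and 6.8 tabulate and list prior medications too, so the drug appears under the wrong heading rather than disappearing. The primary safety analysis is the incidence of treatment-emergent adverse events with Clopper-Pearson intervals, which uses no medication dates.

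The case can also be pressed on frequency. Protocol 5.6 requires start and stop dates in the eCRF and collects changes at every visit, so year-only dates for drugs stopped during the trial should be uncommon. Drugs flagged ongoing are unaffected, and a complete start or stop date after consent is enough to make a drug concomitant. The 75% figure applies only to stops soon after consent and falls to 21% and 14% over longer spans.

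All of this stands and limits the point. It does not remove it: SAP 6.1 and 5.1 together still give a label that contradicts SAP 6.8.

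**Conclusion.** The point holds as a minor defect. One earliest-date rule for start and stop dates alike, combined with the SAP 5.1 label, classes some drugs taken after consent as past, and it can place a stop date before a complete start date. Given a partial stop date, a drug not flagged ongoing, a start before consent and evenly spread dates, the rates are those worked out above: with the day missing, high near consent and 14% over the whole study; with day and month missing, about 85% over the whole study. These are conditional rates. The number of partial dates is not given, so the number of affected records cannot be estimated.

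The effect is confined mainly to the prior and concomitant medication tables. The reading that prohibited-medication deviations are missed, or that per-protocol membership is distorted, goes beyond the text. What can fairly be said is that the SAP leaves unstated which dates the deviation review uses.

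**What to change.** In SAP 6.1, separate the two kinds of date:

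- **Partial start dates:** keep the earliest possible day.
- **Partial stop dates:** use the last day of the month, or 31 December if the month is missing, capped at the last study visit and never before the start date.

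In SAP 5.1, label a drug that is not flagged ongoing as concomitant unless its known date parts show that it stopped before consent. This brings 5.1 into line with 6.8 and also settles records whose stop date is wholly missing, which 6.1 leaves unimputed.

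In SAP 4.3 item 4, state that the review uses recorded dates, not imputed ones. Running it on latest-date imputations could raise false flags for drugs that stopped before the window.

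The cost is a few sentences and a few lines of code. The downside is small: some drugs that truly stopped before consent will be tabulated as concomitant. One limit remains. With earliest-date starts, a drug begun during the trial with a partial start date may still appear as pre-existing in the SAP 6.8 split, although it will be counted as concomitant.

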5.4 Blinding and Breaking the Blind

The study will be performed in a single-blind ([subject blind] Screening Placebo Run-In Period) and a double-blind (Treatment Period) manner. All study drugs will be supplied in identical HDPE bottles and will be similar in colour, smell, taste, and appearance, thereby enabling single- and double-blind conditions.

During the Treatment Period, the study blind should not be broken except in a medical emergency (where knowledge of the study drug received is essential for the treatment of the emergency) or due to a regulatory requirement (eg, expedited reporting). If required for medical emergency, the EDC system will be used to break the blind.

If the blind is broken, the date, time and reason will automatically be recorded in the subject's electronic case report form (eCRF). An automated email notification from EDC will be sent to the Sponsor/Medical Monitor in the event that the blind is broken.

If an Investigator, site personnel performing assessments, or subject, is unblinded, the subject must be withdrawn from the study and procedures accompanying withdrawal are to be performed. In cases where there are ethical reasons for the subject to remain in the study, the Investigator must obtain specific approval from the appointed CRO for the subject to continue in the study.

The overall randomization code will be broken only for reporting purposes. This will occur once all interim/final (as appropriate) clinical data have been entered onto the database and all data queries have been resolved and database lock has been approved.

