8.11 Missing Data

As a sensitivity analysis, missing data will be addressed with a multiple imputation method for the efficacy endpoints only. Details of the imputation method will be identified in the SAP prior to unblinding the data which will include the seed for the imputation, the number of imputations, and how the imputations will be randomly selected. As the only term in the efficacy analysis that should be missing is the change from baseline, the imputation will be a simple imputation on this variable with no covariates. In the event other values are missing, they too will be imputed using simple multiple imputation methods with no covariates in the imputation algorithm. This is consistent with an assumption of missing completely at random (MCAR). This method is selected over single imputation methods as the anticipated placebo effect is expected to be considerable.

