6.3 General Methodology

Safety

Safety data will be presented and analysed using the Safety Population.

The primary safety analyses include all treatment emergent adverse events defined as any AE started after Visit 2. The analysis will be carried out with point estimates and Clopper Pearson 95% confidence intervals.

Descriptive statistics will be provided for all variables in the summary tables by treatment group according to the type of variable summarised.

Quantitative variables will be summarised by using n (number of subjects per group), arithmetic mean, standard deviation (SD), median and range (minimum and maximum).

Categorical variables will be summarised by using frequency distributions and percentages.

The number of Adverse Events and the number and the percentage of patients experiencing those events, will be summarised by treatment group. Differences between groups will be evaluated using Chi-square test or Fisher's exact test. Subgroup analysis of differences between groups of AEs will be performed separately for patients who had an adverse event while on the 10mg dose (AE started from Visit 2 and Visit 3), 20 mg dose (AE started from Visit 3 and Visit 4) and 30 mg dose (AE started from Visit 4 and Visit 6). Subjects with adverse events who deviated from the protocol dosage will be highlighted in the footnotes.

Shift tables will be used to describe the evaluation of clinical significance for laboratory values, 12-Lead ECG and physical examination.

For all analyses, hypothesis testing will be carried out at the alpha = 0.05 level (two-sided) when comparing treatments. P-values will be rounded to three decimal places. Statistical significance will be declared if the rounded p-value will be less than or equal to 0.05.

Efficacy

For the PP efficacy analysis of incontinence episodes, only valid efficacy endpoints at Visit 6 will be used. For the ITT efficacy analysis of incontinence episodes, valid and imputed endpoints at Visit 6 will be used. The imputation method is described in section 6.1. No LOCF from baseline will be used for any efficacy analysis.

Descriptive statistics will be provided for all variables in the summary tables by treatment group according to the type of variable summarised.

Quantitative variables will be summarised by using n (number of subjects per group), arithmetic mean, standard deviation (SD), median and range (minimum and maximum).

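### SAP 6.1, read literally, runs the imputation while arm is unknown and never names arm as a covariate; if arm is omitted, the imputed ITT effect shrinks toward no difference by roughly the missing fraction

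*SAP*

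**What the plan says.** SAP 6.1 introduces the handling of missing Visit 6 counts with the sentence "The cases where the total number of incontinence episodes is missing will be addressed prior to unblinding with the following multiple imputation process". It proposes predictive mean matching (PMM), a regression-based method "using a set of observed values from cases deemed to be similar to the missing case based on a set of covariates". The covariates are not listed, and randomised arm is neither included nor excluded. The section adds: "This methodology is consistent with an assumption of Missing at Random". The seed is set to 1. The number of imputations is tied to the percentage missing, without a rule.

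The imputed values feed the ITT efficacy analysis. SAP 6.3 states: "For the ITT efficacy analysis of incontinence episodes, valid and imputed endpoints at Visit 6 will be used". SAP 6.9 point 1 then fits an ANCOVA to the log of the Week 8 to baseline ratio, with dose and centre as factors and baseline episodes as covariate. SAP 6.2 names the same terms, but for the ANCOVA only.

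Protocol 8.11 gave imputation a different role and form: "As a sensitivity analysis, missing data will be addressed with a multiple imputation method for the efficacy endpoints only", and "the imputation will be a simple imputation on this variable with no covariates". On timing it says: "Details of the imputation method will be identified in the SAP prior to unblinding the data". Protocol 5.4 keeps the overall randomisation code closed until the clinical data are entered, "all data queries have been resolved and database lock has been approved". Neither document describes masked arm codes for use in imputation.

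SAP 6.1 and 6.9.1 also plan ITT analyses without imputation, and SAP 6.3 restricts the per-protocol analysis to observed Visit 6 values.

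**The concern.** An imputation model should contain the term whose effect the analysis model estimates. If arm is absent, a missing litoxetine subject and a missing placebo subject with the same covariates draw from one pooled set of donors. Their imputed counts then differ by arm only through any arm information in the covariates. Baseline and centre cannot supply it, because arm was randomised. Adding such values to both arms pulls the estimated difference toward zero.

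At stake is the imputed ITT estimate for incontinence episodes, which the SAP treats as the ITT result, with the unimputed version labelled a sensitivity analysis. If the two differ because of how the imputation was built, the gap could be misread as sensitivity to dropout. No safety conclusion is affected.

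**Working it through.** **Plan figures.** About 78 randomised 2:1 (SAP 3.1, 3.2) gives 52 litoxetine and 26 placebo. The plan states no attenuation and no missing-diary rate, so the missing totals below are assumptions. SAP 3.1 gives 30% dropout and 60 evaluable, which do not agree: 78 × 0.70 = 54.6, whereas 78 − 60 = 18 is 23.1%. The pair 78 and 60 arises from 60 × 1.30 = 78. I use 18 as the main case, 8 as a milder assumed case, and 23 (78 × 0.30 = 23.4) for the dropout rate as stated.

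**Formula.** Let δ be the true log ratio, mL and mP the missing fractions by arm, and wL and wP the arm shares among observed subjects (the donors). Assume missingness at random within arm and no covariate that carries arm information. A pooled donor then carries, on average, wL·δ.

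- Litoxetine mean shift after imputation: (1 − mL)·δ + mL·wL·δ
- Placebo mean shift after imputation: mP·wL·δ
- Difference: δ·(1 − mL·wP − mP·wL)

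The shrinkage is therefore mL·wP + mP·wL. If mL = mP = m, it equals m, because wL + wP = 1: 8/78 = 10.3% and 18/78 = 23.1%.

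| Missing (litoxetine + placebo) | mL·wP + mP·wL | Shrinkage |
|---|---|---|
| 5 + 3 | (5/52)(23/70) + (3/26)(47/70) | 10.9% |
| 8 + 0 | (8/52)(26/70) | 5.7% |
| 0 + 8 | (8/26)(52/70) | 22.9% |
| 12 + 6 | (12/52)(20/60) + (6/26)(40/60) | 23.1% |
| 18 + 0 | (18/52)(26/60) | 15.0% |
| 9 + 9 | (9/52)(17/60) + (9/26)(43/60) | 29.7% |
| 0 + 18 | (18/26)(52/60) | 60.0% |
| 15 + 8 | (15/52)(18/55) + (8/26)(37/55) | 30.1% |

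For scale, an assumed true ratio of 0.70 (log −0.357) would appear as exp(−0.357 × 0.769) = 0.76 at 12 + 6.

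**Simulation check.** 800 trials, 10 imputations, 5 donors, PMM on baseline only, then ANCOVA on the log ratio with arm and baseline. Assumed inputs: true log ratio −0.5, residual SD 0.8. Centre was not simulated.

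| Split | Shrinkage, arm omitted | Shrinkage, arm included |
|---|---|---|
| 5 + 3 | 10.9% | 1.5% |
| 18 + 0 | 14.1% | 0.3% |
| 12 + 6 | 23.1% | 0.4% |
| 9 + 9 | 30.0% | 1.2% |

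A second simulation with other assumed inputs (true ratio 0.70, log SD 0.8 plus Poisson counts, 20 imputations) agreed for the omitted-arm case: 77% of the full-data effect was kept at 12 + 6. With arm in the model 95% to 100% was kept, and the unimputed ITT analysis kept 99% to 101%.

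**The case against.** **Exclusion of arm is an inference.** No sentence says that arm is left out. Protocol 8.11 refers to the time before unblinding only as the deadline for specifying the method, and SAP 6.1 supplies several of those details. The next section, SAP 6.2, lists covariates that include dose. This stands as a real alternative reading. It does not settle the matter: the SAP sentence says that the missing cases themselves are dealt with before unblinding, SAP 6.2 is written for the ANCOVA, and on either reading arm is not named.

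**Other covariates might carry arm information.** Post-randomisation covariates such as adverse events would reduce the pull. This stands as a limit on the figures.

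**Shrinkage might be deliberate conservatism.** The SAP defines no estimand, so it does not say that dropouts keep the drug effect. But it does state Missing at Random, and it states no rule under which dropouts lose the effect. Pooled donors would not implement such a rule cleanly either, since missing placebo subjects would be given part of the drug effect.

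**The plan has a safeguard.** The unimputed ITT and per-protocol analyses are free of this mechanism, and in simulation the unimputed ITT did at least as well as imputation with arm included. This stands and limits the harm. What remains is that the imputed result is the main ITT one, and a gap between the two could be misread.

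**Conclusion.** The concern holds in conditional form. Followed literally, SAP 6.1 sets a timing rule that keeps arm out of an imputation whose values are then used to estimate the arm effect. On the milder reading, the SAP leaves that choice open.

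If arm is omitted, the imputed ITT log ratio shrinks by about the missing fraction when missingness is similar by arm: about 10% with 8 missing (6% to 23% by split) and 23% with 18 missing (15% if all are on litoxetine, 60% if all are on placebo). These figures rest on assumed missing totals, arms of 52 and 26, missingness at random within arm, and covariates without arm information. Two features of the plan could change them. The ITT set in SAP 4.1 needs a dose and a valid baseline, so the arms may be smaller. Early-termination visits follow the Visit 6 procedures, diary collection included (Protocol 7.1.6 and Appendix 2 note 4), so fewer counts may be missing and the shrinkage smaller.

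A reader might infer that the SAP excludes arm and that the efficacy result is therefore biased by a known amount. The documents do not support that: exclusion depends on the literal reading, and the amount depends on a missing rate and a split by arm that they do not give. Nor is the trial's main conclusion at risk, since safety is primary and efficacy is exploratory. The point is worth fixing because the correction costs almost nothing.

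**What to change.** In SAP 6.1, replace the sentence that places the imputation itself before unblinding. Suggested content: the imputation code, number of imputations and covariate list are locked before unblinding, and the imputation is run after the code is broken, or before it with masked arm codes. With 2:1 allocation, group sizes would reveal masked codes, so running after the code is broken is simpler. State that the PMM model includes randomised arm and baseline episodes, or that imputation is done within arm. The seed is already fixed.

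Two additions are optional documentation: a statement that the ANCOVA results are combined across imputations by Rubin's rules, and a line in SAP 1.5 recording that imputation moved from a no-covariate sensitivity analysis in Protocol 8.11 to the ITT analysis.

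The cost is two or three sentences, with no new subjects or data and no change to the ANCOVA. Locking the code and covariates beforehand protects against choices made with knowledge of the results.
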